### **5.2.3                   Guidance for Determination of Cirrhosis**

All patients will be evaluated for the presence of cirrhosis and the final assessment will be made by the site PI or clinician designee. The presence of cirrhosis is defined at screening by biopsy and/or a combination of clinical, laboratory, elastography, and imaging criteria established *a priori*. For post-transplant recipients, cirrhosis determination will be made based on medical records post allograft.

Patients will be determined to have cirrhosis if they have:

- 1) evidence of stage 4 (Metavir) fibrosis by liver biopsy at any time prior to screening;
- 2) evidence of stage 3 (Metavir) fibrosis by liver biopsy at any time prior to screening with any ONE of the following criteria (for post-transplant recipients, biopsy staging must be from the allograft);
  - platelet count  $<140 \times 10^9/L$ ,
  - presence of esophageal varices on esophagogastroduodenoscopy at any time prior to screening,
  - evidence of cirrhosis and/or portal hypertension by imaging studies at any time prior to screening,
  - FibroTest®  $>0.75$ ,
  - Vibration-Controlled Transient Elastography (VCTE)  $>12.5$  kPa, or equivalent magnetic resonance elastography (MRE) compatible with stage 4 fibrosis

3) in the absence of liver biopsy, any TWO of the following criteria:

- platelet count <140x 10^9/L during screening,
- presence of esophageal varices on esophagogastroduodenoscopy at any time prior to screening,
- evidence of cirrhosis and/or portal hypertension by imaging studies at any time prior to screening,
- FibroTest® >0.75,
- AST:platelet ratio index (APRI) >2 during screening
- Vibration-Controlled Transient Elastography (VCTE) >12.5 kPa, or equivalent MRE compatible with stage 4 fibrosis

If subjects do not meet any of the above definitions of cirrhosis, they will be considered non-cirrhotic.

#### **5.2.4 Prior and Concomitant Therapy**

Any medication or vaccine (including over-the-counter or prescription medicines, vitamins and/or herbal supplements) that the subject is receiving from the time of signing the consent, through the Treatment Period, and 30 days after study drugs are stopped, must be recorded in the medical record along with the reason for use according to standard medical care. Where the reason for use of a concomitant medication or the start/stop date is missing from the submitted medical records, the site will be queried. For the Main study, the investigator/designee should review all concomitant medications for any potential interactions with G/P via the DDI tool and the MAVYRET™ Prescribing Information. For the Retreatment sub-study, the investigator/designee should review all concomitant medications for any potential interactions with G/P via the DDI tool and the MAVYRET™ Prescribing Information, and also should review all concomitant medications for any potential interactions with sofosbuvir utilizing the Sovaldi™ Prescribing Information.

During the Post-Treatment Period, all concomitant medications taken will be recorded in the

medical record until 30 days following the last dose of study drugs. Only medications taken for SAEs and for treatment of HCV will be recorded thereafter.

The medical monitor should be contacted if there are any questions regarding concomitant or prior therapies.

Subjects with HIV-1/HCV co-infection must be on a stable, qualifying HIV-1 ART regimen for at least 8 weeks prior to Screening. If on an HIV-1 ART regimen, it must include at least one of the ARV agents as per Inclusion Criterion 9 (Section 5.2.1).

Subjects will maintain the same dose and dosing interval of their HIV-1 ART regimen upon initiating the study drugs regimen. Subjects should remain on the same HIV-1 ART regimen for the entire Treatment Period. Any change in the HIV-1 ART regimen during the Treatment Period must be discussed with the medical monitor prior to the change, unless the change is being made to address an immediate safety concern.

Subjects receiving any other HIV-1 ART in addition to those listed in Inclusion Criterion 9 (Section 5.2.1) would not be eligible for enrollment in the study.

#### **5.2.4.1                    Prior HCV Therapy**

Subjects must be HCV treatment-experienced with an NS5A-inhibitor+SOF with or without RBV. The subject may also have had an additional past treatment with any HCV regimen that did not include administration of a protease inhibitor.

For subjects who had multiple HCV treatment courses, the categorization of previous response category will be based on the NS5A inhibitor+SOF treatment.

### **5.2.4.2      Concomitant Therapy**

Subjects should be on stable doses of concomitant medications for at least 2 weeks prior to the initiation of study drugs. The investigator should confirm that a concomitant medication/supplement can be safely administered with study drugs. Some concomitant medications may require dose adjustments due to the potential for drug-drug interactions.

During the Post-Treatment Period, investigators should reassess concomitant medications/supplements, and subjects may resume previously prohibited medications/supplements or revert to pre-study doses 2 weeks following discontinuation of study drugs as applicable.

### **5.2.4.3      Prohibited Therapy**

Subjects must be able to safely discontinue any prohibited medications or supplements listed in **Table 4** at least 2 weeks or 10 half-lives (whichever is longer) prior to the first dose of any study drug and not use these during the entire Treatment Period and for 2 weeks following discontinuation of study drugs.

**Table 4.      *Prohibited Medications and Supplements***

---

#### **Medication or Supplement Name**

red yeast rice (monacolin K), St. John's Wort
Carbamazepine, phenytoin, pentobarbital, phenobarbital, primidone, rifabutin, rifampin
Atorvastatin, lovastatin, simvastatin*
Astemizole, cisapride, terfenadine
Ethinyl estradiol
Atazanavir, darunavir co-administered with ritonavir, darunavir/r, lopinavir/r, efavirenz, etravirine, tipranavir/r, nevirapine
Azathioprine-if subject is taking RBV
Amiodarone- Applicable to Retreatment sub-study subjects receiving sofosbuvir

\* Some HMG-CoA reductase inhibitors (including atorvastatin, lovastatin, or simvastatin) should not be taken with the study drugs. Subjects receiving these statins should either switch to pravastatin or rosuvastatin prior to the first dose of study drugs or may interrupt statin therapy throughout the treatment period and until 14 days after the last dose of study drug, based on investigator's judgment. If switching to or continuing pravastatin or rosuvastatin, it is recommended to reduce the pravastatin dose by 50% or limit the rosuvastatin dose to 10 mg QD when taking with the study drugs.

Use of high dose (0.035mg) ethinyl estradiol containing oral contraceptives with G/P combination was associated with asymptomatic ALT increases (one Grade 3, and one Grade 2) without concurrent bilirubin increases in 2 healthy female subjects. Therefore, hormonal contraceptives (including oral, topical [including vaginal rings], injectable or implantable varieties) containing any ethinyl estradiol may not be used from 2 weeks prior to the first dose of study drug until 2 weeks after the end of study drug dosing. Progestin-only contraceptives, such as those containing norethindrone, desogestrel, or levonorgestrel, without ethinyl estradiol, may be used with G/P.

Post-menopausal hormone replacement therapy, such as with esterified or conjugated estrogens, i.e., not containing ethinyl estradiol, may be used with G/P at the discretion of the Investigator.

For HCV/HIV-1 coinfecte subjects, the investigator must refer to the current package insert(s) or product label(s) of a subject's ART regimen for a complete list of medications prohibited to be used with those drugs, which should not be used at least 2 weeks prior to the first dose of any study drug and not use these during the entire Treatment Period and for 30 days following discontinuation of study drugs. G/P is not recommended for use in patients requiring stable cyclosporine doses  $> 100$  mg per day. G/P may be initiated in subjects receiving cyclosporine  $\leq 100$  mg per day and cyclosporine doses may be adjusted up to 400 mg per day following standard therapeutic monitoring practices.

## 5.3

**Efficacy, Pharmacokinetic, Pharmacogenetic and Safety Assessments/Variables**

## 5.3.1

**Efficacy and Safety Measurements Assessed and Flow Chart**

Study procedures described in this protocol are summarized in **Table 5** and **Table 6**

**Table 5. Study Activities – Treatment Period for Main study and Retreatment sub-study**

*Subjects assigned to a 12-week treatment duration will not complete the Wk16 EOT visit. Any patient eligible to receive treatment in the Retreatment sub-study will be assessed as noted for screening and according to ALL on-treatment evaluations outlined in the activities table.*

Activity	Screening	Day 1 a	Wk 4	Wk 8	Wk 12 or EOT	Wk 16 EOT	Premature D/C b
STANDARD OF CARE and documented in Medical Record							
Demographics & Medical History (including history of hepatic decompensation and Prior HCV Therapy)	X						
Physical Exam & Child-Pugh Score	X						
Vital Signs, Weight, Height d	X						
Cirrhosis Determination (per Section 5.2.3)	X						
Concomitant Medication Assessment	X n						
Adverse Event/Serious Adverse Event Assessment e	X m						
HCC Screening documentation as applicable to subjects with cirrhosis (within 6 months of screening) f	X						
For HIV co-infected subjects, CD4+ & HIV RNA results obtained locally (per Inclusion 9)	X p						

## Protocol

B16-439 November 20, 2018

Activity	Screening	Day 1 a	Wk 4	Wk 8	Wk 12 or EOT	Wk 16 i EOT	Premature D/C b
REQUIRED ASSESSMENT outside of Standard of Care							
Informed Consent c	X						
Verification of Eligibility/Randomization	X j						
Hematology/Chemistry/PT/INR g	X	X	X	X	X	X	X
Pregnancy Test (serum [s] g urine [u] k ) for WOCBP only	X (s)	X (u)	X (u)	X (u)	X (u)	X (u)	X (u)
HCV Genotype and Subgenotype; HBV serologies g	X o						
HIV Ab g,l	X o						
FibroTest and APRI g,h	X o						
HCV RNA Samples g	X	X	X	X	X	X	X
HCV Resistance Sample g		X	X	X	X	X	X
Archive Plasma Sample g	X	X	X	X	X	X	X
Study Drugs Dispensed		X	X	X	X i		
Randomization Request submitted centrally at least 5 business days prior to planned Day 1	X j						
Perform Study Drug Accountability and Review of Study Drug Adherence			X	X	X	X	X
Authorization Request for Retreatment	X j						
Upload signed central lab reports evaluating clinical significance of abnormal results	X	X	X	X	X	X	X
Medical Records & Blood sample collection Verification Worksheet and Records Submission	X	X	X	X	X	X	X

Wk = Week; EOT = End of treatment; D/C = Discontinuation

- a. All procedures to be performed prior to first dose
- b. Subjects who prematurely discontinue the Treatment Period should return to the site to complete the Premature D/C Visit Procedures (preferably prior to the initiation of any

## Protocol

B16-439 November 20, 2018

---

other anti-HCV therapy).

- c. Subjects need to sign an IRB/IEC approved informed consent for the study prior to performing any screening or study-specific procedures. All re-treatment substudy subjects will be required to sign additional informed consent inclusive of re-treatment substudy information.
- d. Height only collected at Main Study Screening
- e. During the treatment period, all SAEs must be collected that occur during the screening period through discontinuation of study treatment and all non-serious AEs must be collected that occur from the time of study drug administration through 30 days after discontinuation of dosing. (see Section 6.1.4).
- f. Subjects with a historical negative Liver Ultrasound, CT or MRI within 6 months prior to screening for main study and within 6 month prior to screening for the Retreatment sub-study are not required to have a screening Liver Ultrasound performed.
- g. Collected for central laboratory processing.
- h. Fibrotest/APRI will only be collected at the screening visit if the subject does not have a qualifying liver biopsy, Fibroscan, or MRE
- i. Only applies if subject assigned to 16-week treatment arm (B or D), and subjects of the Retreatment sub-study
- j. Main study: Site must submit documentation that the subject meets all eligibility criteria to the CCC at least business 5 days prior to their Day 1 visit. Randomization will be performed by the CCC. Retreatment sub-study: Prior to starting treatment, the site will upload subject redacted records to REDCap for verification of eligibility by the CCC. Prescription for Sofosbuvir +/- RBV must be included in upload.
- k. If the urine pregnancy result is positive, site must confirm immediately with a serum test collected through the central laboratory
- l. HIV Ab collected only in subjects without historical positive HIV antibody.
- m. Non-serious Adverse Events will not be collected between Post-Treatment Week 12 of Main Study and first dose of Retreatment sub-study Dosing Period. Serious Adverse Events will not be collected between Post-Treatment Week 12 of the Main Study and date of informed consent for the Retreatment sub-study
- n. Concomitant medications will not be collected between Post-Treatment Week 4 of Main Study through 14 days prior to Screening for Retreatment sub-study
- o. Not required for Retreatment sub-study
- p. As available for abstraction per SOC in the submitted redacted medical records.

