**5.1.2 Protocol Required Assessments (not billed as standard of care Table 5 and Table 6)**

1. All study required safety and efficacy labs outside of standard of care, including Fibrotest and APRI (if assignment of cirrhosis status is unable to be made by site PI).
2. Baseline NS3 and NS5A sequencing
3. NS3, NS5A and \*NS5B sequencing at evidence of virologic failure
4. G/P, RBV, \*SOF are provided to patients free of charge

\* For Retreatment sub-study only

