**Table 8. Clinical Laboratory Tests**

Hematology	Clinical Chemistry
White Blood Cell (WBC) count	Albumin
Red Blood Cell (RBC) count	Alkaline phosphatase
Hemoglobin	Alanine aminotransferase (ALT)
Hematocrit	Aspartate aminotransferase (AST)
Platelets	Bilirubin, Direct
Neutrophils	Bilirubin, Indirect
Lymphocytes	Bilirubin, Total
Monocytes	Blood Urea Nitrogen (BUN)
Eosinophils	Calcium
Basophils	Carbon Dioxide
Bands, if detected	Chloride
Prothrombin Time (PT)	Cholesterol
INR	Creatinine
Other Tests	
Urine and Serum Human Chorionic Gonadotropin (hCG) for females (pregnancy)	Glucose
HCV RNA	Phosphorus
HCV genotype and subtype	Potassium
HBsAg, Hep B Core Ab-Total, Hep B Surface Ab	Sodium
reflex HBV DNA a	Total protein
HIV 1-2 b	Uric Acid
APRI and Fibrotest	eGFR by MDRD

aIf HBsAg neg, Hep B Core AB-Total positive at ScreeningbOnly required for subjects without historical positive test result for HIV Ab

For any laboratory test value outside the reference range that the investigator considers to be clinically significant:

- The investigator will repeat the test through the central laboratory to verify the out-of-range value.
- The investigator will follow the out-of-range value to a satisfactory clinical resolution.
- A laboratory test value that requires a subject to be discontinued from the study, a dose modification of RBV, or requires a subject to receive treatment will be recorded as an adverse event.

The management of laboratory abnormalities that may occur during the study is described in Section 6.1.6

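### Table 5 note h, Section 5.1.2 and Section 5.2.3 disagree on when FibroTest is drawn, so a subject with cirrhotic-range elastography can default to the non-cirrhotic stratum

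*Protocol*

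**What the plan says.** Three current parts of the Protocol govern how cirrhosis status is established and when FibroTest and APRI are obtained.

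- **Section 5.2.3** sets the rule for a subject without a biopsy: "in the absence of liver biopsy, any TWO of the following criteria". The six criteria are low platelets, varices, imaging evidence, FibroTest, APRI and elastography. The last two read "AST:platelet ratio index (APRI) >2 during screening" and "Vibration-Controlled Transient Elastography (VCTE) >12.5 kPa, or equivalent MRE compatible with stage 4 fibrosis". The default is "If subjects do not meet any of the above definitions of cirrhosis, they will be considered non-cirrhotic". On who decides, "the final assessment will be made by the site PI or clinician designee".
- **Section 5.3.1, Table 5, note h** limits collection: "Fibrotest/APRI will only be collected at the screening visit if the subject does not have a qualifying liver biopsy, Fibroscan, or MRE". It does not say what makes a result qualifying.
- **Section 5.1.2** lists the protocol-required laboratory tests, "including Fibrotest and APRI (if assignment of cirrhosis status is unable to be made by site PI".

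Table 5 marks hematology and chemistry at Screening for everyone. Table 8 puts platelets and "Aspartate aminotransferase (AST" on those panels.

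**The concern.** Note h treats a Fibroscan or MRE result as a reason not to collect FibroTest. Under Section 5.2.3, an elastography result can never settle cirrhosis by itself when there is no biopsy. The schedule can therefore leave uncollected the test that would have supplied the second criterion, and the default sentence then labels the subject non-cirrhotic.

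The label carries weight. It decides whether the subject is randomised 2:1 to Arms A/B or 1:1 to Arms C/D, which regimens are possible, and which of the two primary comparisons the subject enters. It also decides whether Inclusion Criterion 6, which requires HCC imaging only in cirrhotic subjects, applies. A subject placed in A/B this way is also lost to the cirrhotic comparison, which is the smaller one (cap of 75 against 150).

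**Working it through.** The protocol states no figure to reproduce here. The check sets the rules side by side and counts logical patterns.

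**Step 1. What each passage requires for a subject with no biopsy and elastography in the cirrhotic range**

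| Passage | Rule | Effect |
|---|---|---|
| Section 5.2.3 | at least 2 of 6 criteria | elastography gives 1; one more is needed |
| Table 5, note h | FibroTest/APRI only if no qualifying biopsy, Fibroscan or MRE | FibroTest not drawn |
| Section 5.1.2 | FibroTest/APRI if the PI cannot assign status | depends on whether the PI regards the default as an assignment |
| Section 5.2.3, default | no definition met means non-cirrhotic | Arms A/B |

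**Step 2. Possible meanings of qualifying**

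- *Above the Section 5.2.3 threshold.* FibroTest is withheld from the subjects who are one criterion short.
- *A technically valid examination, whatever the result.* A subject below the threshold with one other criterion also loses FibroTest as the possible second.
- *Enough to settle status under Section 5.2.3.* Elastography alone never is, so naming Fibroscan and MRE in the note has no function.

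No reading gives the elastography exemption a sound purpose.

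**Step 3. Counting patterns.** Fix elastography as positive. The other five criteria (platelets, varices, imaging, FibroTest, APRI) can each be present or absent, which gives 2^5 = 32 patterns. A subject is cirrhotic if 1 + (number of other criteria documented) ≥ 2.

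| Inputs available | Classified cirrhotic | Lost against all inputs |
|---|---|---|
| All five | 31 of 32 | none |
| FibroTest and APRI both missing | 28 of 32 | 3: APRI only; FibroTest only; both |
| FibroTest missing, APRI calculated from screening labs | 30 of 32 | 1: FibroTest only |

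These count logical combinations, not patients.

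**Step 4. The remaining case.** Take no biopsy, elastography above 12.5 kPa, platelets at or above 140, no varices or imaging evidence on record, APRI at or below 2, and a FibroTest that would have exceeded 0.75. Documented criteria: 1, so non-cirrhotic. With FibroTest drawn: 1 + 1 = 2, so cirrhotic.

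**Step 5. How far APRI helps.** The protocol does not print the APRI formula. Assume the usual one, APRI = 100 × (AST/ULN) / platelets. Then APRI > 2 requires AST/ULN > 2 × platelets / 100. That is 2.8 at platelets of 140, 3.0 at 150, 4.0 at 200 and 5.0 at 250. When the platelet criterion is not met, APRI supplies the second criterion only if AST is well raised, so it closes part of the gap and not all of it.

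**The case against.** The strongest reply is that this is a wording gap with backstops. Note h says qualifying, not any, so it could be read together with Section 5.1.2. The site PI makes the final assessment and may ask for FibroTest when unsure. Varices and imaging evidence count from any time before screening, and sites submit 24 months of records plus older liver-disease records. APRI needs no separate draw.

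Much of this stands, and it makes the affected group narrow. It does not close the gap. A PI who applies the default sentence has assigned a status, so Section 5.1.2 does not clearly trigger, and note h says the tests are collected only in its own circumstances. Section 5.1.3 asks for EGD and imaging records only if those were done. Central eligibility verification works from submitted records and cannot see a test that was not drawn.

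A reader might infer several stronger things that the protocol does not support:

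- *That APRI is withheld.* Its components are unrestricted screening labs, so the information actually lost is FibroTest.
- *That having a Fibroscan leaves the subject worse off than not having one.* Without it, the elastography criterion disappears too, and a positive FibroTest would again be only one criterion.
- *That every subject with elastography as the sole criterion is a misclassified cirrhotic.* Under Section 5.2.3, one criterion is not cirrhosis. Only those whose undrawn FibroTest would have been positive change category.
- *That the rise in the A/B failure rate can be computed.* No source gives the misplaced fraction. The Section 3.4 figure of 30/31 for non-cirrhotic subjects also includes four outside the 12- and 16-week G/P groups (12/13 + 14/14 = 26/27).
- *That the A–B difference is biased.* Misplaced subjects are randomised 2:1 within A/B like everyone else, so a shared change in failure rate does not by itself bias the difference.
- *That the compensation checks are bypassed altogether.* Table 5 schedules Child-Pugh at Screening for all, and the bilirubin and albumin exclusions apply to all. The consequence that stands is the loss of the HCC-imaging requirement.

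**Conclusion.** The inconsistency is real and worth correcting. Followed as written, the protocol can place a subject in the non-cirrhotic stratum because a test that feeds its own two-criteria rule was not drawn. In logical terms, 1 of 32 patterns is affected if sites calculate APRI from screening labs, and 3 of 32 if they do not. How many subjects that means cannot be estimated from the protocol; it is probably few.

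The consequences are the wrong stratum, randomisation ratio and primary comparison, and the loss of the HCC-imaging requirement for those subjects. What suffers is the make-up of the two populations; no bias in either treatment difference has been demonstrated. The conclusion assumes that sites follow note h as written and that PIs apply the default sentence rather than invoke Section 5.1.2.

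**What to change.** Reconcile note h, Section 5.1.2 and Section 5.2.3 so that the inputs to the existing rule are available before the non-cirrhotic default applies:

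1. Calculate APRI from screening AST and platelets for every subject without a biopsy.
2. Replace the undefined qualifying exemption in note h with a trigger tied to whether Section 5.2.3 is already satisfied on documented criteria, so that an elastography result alone does not switch off FibroTest.
3. State the same trigger in Section 5.1.2.

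The thresholds and the two-criteria rule in Section 5.2.3 stay as the sponsor set them. The cost is a short edit in two places, a calculation from labs already drawn, and a few added FibroTest assays at the central laboratory, where the test is already in the schedule.
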